The available research indicates a strong positive correlation between patient education and outcomes. However, there is limited literature on the direct influence of pain management education on patients' recovery, engagement, pain relief, adverse effects, safety, and long term outcomes. These gaps are consistent with the identified research gaps from the NIH and APS. The use of technology in clinical practice and patient education, such as mobile applications, patient portals, and iPads, are only just beginning to be explored in the last five to ten years. Further research is needed to understand the effectiveness, barriers, and use of eHealth delivery models. One barrier to eHealth delivery is adoption and use of technology in the elderly populations. The elderly population has lagged in the acceptance and adaptation to technology. Only 59% of seniors use the internet and computer, compared to 86% of all adults (Smith, 2014). The adoption of technology in this population is potentiated by physical challenges (arthritis, and vision changes), skeptical attitudes about the benefits of technology, and difficulty with learning how to use digital devices. However, a paradigm shift is occurring with a 6% annual increase in the number of seniors using technology (Smith, 2014). This trend is anticipated to continue, making technology less of a challenge in health information delivery. The average age of patients undergoing TJA surgery is 67 years of age. As such, consideration and further research into the adoption of eHealth delivery in this population is necessary. Additionally, each education delivery method poses several advantages and disadvantages. Verbal 1:1 education is patient centered and allows for direct interaction and questions yet is costly, time consuming, and is associated with limited memory recall (Knowles, Holton, Swanson, 2011). This style of education is often used in conjunction with written text in the form of booklets or pamphlets. Written education allows for mass distribution of educational content but is associated with printing expenses and low patient compliance (Knowles, Holton, Swanson, 2011). Conversely, internet based education is interactive, easily accessible, simple, and visually appealing (Knowles, Holton, Swanson, 2011). Depending on an organization's technological capabilities, internet based education may not be attainable due to technical limitations and cost (Knowles, Holton, Swanson, 2011). The research study proposed here seeks to understand the difference and effectiveness of educational methods and delivery mechanisms using mobile applications compared to standard education delivery (verbal and written) to determine the impact on pain outcomes, pain experience, patient participation, and opioid requirements.

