The target population is adult patients undergoing elective, lower extremity total joint arthroplasty (TJA). Candidates for inclusion are adult patients over the age of 18 years undergoing surgical intervention and inpatient care for one of the following procedures, total hip arthroplasty (THA) (primary, bilateral, and revision) and total knee arthroplasty (TKA) (primary, bilateral, unicompartmental, and revision). Patients must be fluent in the English language. Patients will be excluded if they are undergoing more complex hip and knee procedures such as implant resections with or without spacer placement, liner exchange, or THA or unipolar hip arthroplasty related to repair of hip fracture. Patients will also be excluded if there are preexisting physical or cognitive limitations that would hinder their ability to use the mobile application.

Sample Size

Assuming a moderate effect size 0.50 (Cohen's d), a power of 80% (0.80), and an alpha of 0.05, 64 participants are needed in each study arm (Polit, 2010). Due to limited time scope, a minimum of 150 patients will be approached for potential participation. If time allows and additional subjects are needed to achieve the desired sample size, additional candidates will be approached to reach the recommended total of 128 patients, divided between the two study arms.

Recruitment and Consent

Eligible patients will be identified using surgeon referral and/or electronic surgical listing reports. Enrollment into the study is completely voluntary. Patients will be recruited at the time of perioperative phone consultation with nursing. This consultation occurs approximately two weeks prior to their scheduled surgical procedure. At this time patients will be introduced to the study by the RN or APRN. If the patient expresses interest, verbal consent will be obtained and documented at the time of the call by the IRB approved consent designees. Consent designees will read the consent script and provide any necessary time to answer the patients' questions. At the time of consent, patients will be informed that there are two study arms and that some subjects will receive enhanced pain management education; however, subjects will not explicitly be informed if they are in the intervention or control arm of the study.

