Enrollment into the study is completely voluntary. Participating in this study poses minimal risk to the participants; all patients will receive the necessary education to meet their care needs and the minimum standard of practice. The potential for risk is that the mode of information/education delivery does not meet the patients' needs and the risk of low acceptance of technology use. In this case, patients in the study arm would be removed from the study and would receive standard education. Pain management in both arms will remain the same; no changes will be made to the process for treating pain using either non-pharmacologic or pharmacologic interventions. Medication orders, medication administration, and pain treatment plans will not be affected by participation in study. As care is today, pain management will be customized to meet the needs of the individual patient.

Oral consent will be obtained, documented, and maintained as part of the research records. No identifiable patient information will be maintained. The only identifiable information collected will be the patients' clinic number. It will be used for tracking purposes only until the data collection process is complete. When the chart audit is complete, the clinic numbers will be removed from the data set and only the predesignated subject number will be used and maintained. At the start of the study the patient will be asked to complete the HIPAA Authorization to Use and Disclose Protected Health Information. The researcher will remain blinded to the type of education delivery that the patient will receive until after enrolment and bed assignment. This will prevent potential bias with inadvertently assigning patients to groups based on characteristics, like age.

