Patients enrolled in the study arm will be given an iPad on admission to the post-surgical unit. The RN will instruct the patient on how to use the iPad and the program. The device will remain with the patient until discharge. The patient, independently or with the nurse, may use the program at any point during the inpatient care experience. The RN will use the iPad to engage patients in their pain management and care. Intervention fidelity will be monitored by requiring the RN to indicate when and how often they observed and/or directly engaged the patient in pain education using the mobile device. A checklist will be available on the patients chart for the RN to complete at the end of each shift through the duration of the patients hospital stay.

Control group. The control group will receive the current standard of care which consists of verbal instruction and pain management pamphlets. At a minimum, the patients will receive two educational pamphlets titled *Your Pain and Discomfort Management Menu* and *Communicating About Your Pain*. The pain management menu is designed to provide the patient with basic pain information with a focus on non-pharmacologic pain interventions. The pain communication pamphlet offers a more comprehensive explanation about pain, assessment of pain (0-10 scale), communicating with the healthcare providers, and pain management options. The content of these two documents is a portion of the education the study patients will receive using the mobile application. These two documents are existing educational material available through the Department of Patient Education. These educational materials were developed by the Department of Anesthesia and Pain Service in conjunction with the Department of Patient Education. Verbal instruction is inconsistent and is nurse dependent. At a minimum the nurse is instructed to provide the two pamphlets to the patient and follow-up with the patient to address any questions. Additional printed education materials are available through the department of patient education and verbal instruction may be tailored based on nursing assessment and patient need. It is important to note that all educational content available to the study participants is available to the control group in different forms or functions. Fidelity to standard of care will be

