Patient demographics and clinical characteristics. Patient demographics and past medical history will be collected as part of the study (Appendix D). Patient demographic variables to be collected include age, race, education level, marital status, and employment status. Specific confounding variables associated with the type of intervention and outcome will be collected including patients' preferred learning style, comfort level with technology, and anxiety. Preferred learning style will be assessed using the three styles of learning reading, seeing, doing, or listening (Bastable, 2008). Comfort level with technology will be assessed using a five-point Likert scale with zero being, "not comfortable at all" and five being "very comfortable." Anxiety associated with anticipated pain will be assessed on ten-point. Relevant past medical and surgical history will also be collected including past major orthopedic surgeries, chronic pain, preoperative use of opioids, and mental health conditions. The patient demographic collection form will be administered using paper and pencil survey. The patient will be given the form when they arrive to the ambulatory orthopedic clinic for their perioperative visit, one to two days prior to their scheduled surgery. It will take participants approximately five minutes to complete the survey.

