Data will be collected at three points in time using paper and pencil survey's and chart audits. The data collection protocol can be found in Appendix G. After completion of the HIPAA form, demographic and past medical history information and pain knowledge survey will be administered in the ambulatory clinic at the time of the perioperative surgical visit. A paper and pencil survey/form will be provided to the patient when they arrive in the clinic for their perioperative appointment and returned to the desk staff when completed.

The intervention will occur on the postoperative inpatient care unit (PCU) starting at the time the patient arrives on the unit from the post anesthesia care unit (PACU). The intervention will continue through the course of care until discharge. At the time of discharge the patient will complete the Revised American Pain Society Patient Outcomes Questionnaire (APS-POQ-R) (Gordon et al., 2010) and the revised knowledge-based Patient Pain Questionnaire (PPQ) (Ferrell & Rivera, 1997; Reynolds, 2009). The use of these two widely used instruments will ensure that the information being collected is highly reliable and valid, truly measuring what the study is seeking to evaluate. These paper and pencil survey's will be provided to the patient prior to discharge and collected from the patient by the staff registered nurse (RN) and/or charge nurse. In addition to training and education on the intervention, staff will receive direction on the data (survey) collection process and requirements. The administration of the post-intervention surveys at the point of care, before the patient has left the study environment, will help to prevent the loss of study participants due to non-response or failure to complete follow-up surveys.

After discharge the researcher will conduct a chart review to collect clinical data including opioid consumption totals, past medical history, anesthesia type, and length of stay. The researcher in addition to one RN will be responsible for chart audit data collection. The RNs will be trained by the researcher on chart audit processes. The RNs will complete the institutions IRB education requirements for staff assisting with research data. A tentative timeline has been developed as a GNATT chart in Appendix H. All collected data from the paper surveys' and chart audits will be entered in to SPSS for analysis. Data storage and management is discussed further under ethical considerations.

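### iPad-arm patients whom the iPad does not suit are removed after assignment, with no control counterpart and no analysis population that keeps them, so the comparison can be biased

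*Combined protocol and SAP*

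**What the plan says.** Recruitment and Consent names two risks of participation: delivery that does not meet the patient's needs, and "the risk of low acceptance of technology use". If either occurs, "patients in the study arm would be removed from the study and would receive standard education".

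The timing follows from Intervention, Study group: "Patients enrolled in the study arm will be given an iPad on admission to the post-surgical unit". By then the bed, and so the arm, has been assigned (Design).

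For controls, Intervention, Control group provides additional printed materials and says that "verbal instruction may be tailored based on nursing assessment and patient need". Nothing there takes a control patient out of the study.

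The Data Analysis Plan compares the groups with an independent t-test, or nonparametric tests if normality fails. It examines baseline differences for possible control but specifies no adjusted model. It names no analysis population, no missing-data method and no follow-up of removed patients.

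**The concern.** The removal rule acts after assignment, in one arm only, and on a trait tied to the intervention. Both units should receive a similar share of patients who would not take to an iPad. Under the rule those patients leave the iPad arm, while their counterparts stay in the control arm.

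The study asks whether mobile delivery does better than standard education in this population. The Significance section says "One barrier to eHealth delivery is adoption and use of technology in the elderly populations" and gives an average age of 67 for these patients. Dropping those in whom delivery fails answers the question for accepters only. It also undercuts a safeguard in the same section, where the researcher is kept blind until bed assignment so that characteristics such as age do not influence the grouping.

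The documents do not establish the direction of bias. It plausibly favours the iPad for knowledge, participation and helpfulness of information, and is less certain for pain scores and opioid use. If removed patients would have had the same outcomes as retained ones, there is no bias.

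**Working it through.** **The plan's own figure.** Sample Size gives d = 0.50, power 80%, alpha 0.05 and 64 per arm. Sidedness is not stated. The two-sided two-sample t-test needs 63.77, so 64 per arm, with power 80.1%. A one-sided test needs about 50, so two-sided is used below.

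**Assumed inputs.** Share of the iPad arm removed, p = 5%, 10% or 20%. Gap in mean outcome between retained and removed patients, g = 0, 0.5 or 1.0 SD. True effect zero, within-arm SD 1.

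**Shift.** With the full arm mean set to zero, p × (removed mean) + (1 − p) × (retained mean) = 0, and retained mean − removed mean = g. The retained mean is therefore p × g, while the control mean stays at zero. The largest shift is 0.20 × 1.0 = 0.20 SD, and 0.20 / 0.50 = 40% of the planned effect.

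**Type I error.** The test statistic is noncentral t with noncentrality p·g / √(1/n₁ + 1/64) and n₁ + 64 − 2 degrees of freedom. Without replacement, n₁ = 64(1 − p), rounded. Example, p = 0.20 and g = 0.5: 0.10 / √(1/51 + 1/64) = 0.533 on 113 df, giving 8.3%.

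| Removed | n₁ vs 64 | g = 0 | g = 0.5 SD | g = 1.0 SD | g = 1.0 SD, replaced to 64 | Power at d = 0.50, not replaced |
|---|---|---|---|---|---|---|
| 5% | 61 | 5.0% | 5.2% | 5.9% | 5.9% | 79.2% |
| 10% | 58 | 5.0% | 5.9% | 8.5% | 8.7% | 78.1% |
| 20% | 51 | 5.0% | 8.3% | 18.4% | 20.2% | 75.2% |

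A simulation of the 20%, 1 SD case (20,000 runs, total SD 1) gave 19.0%, hence about 18–19%.

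**Replacement.** Sample Size says that, if time allows, "additional candidates will be approached to reach the recommended total of 128 patients". That restores power but not comparability. The shift is unchanged and the test becomes slightly more sensitive to it.

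**Adjustment for technology comfort.** Under Instruments, "Comfort level with technology will be assessed using a five-point Likert scale" before surgery in both arms. Acceptance, comfort and outcome were simulated as correlated normal variables. The lowest 10% or 20% on acceptance were removed from the iPad arm, and the arms were compared adjusting for comfort. If comfort fully determines acceptance (correlation 1.0), essentially none of the shift remains. At assumed correlations of 0.8 and 0.5, about 40% and 80% remain. These runs used an acceptance–outcome correlation of 0.3. Repeating them at 0.55 gave the same shares.

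**The case against.** The strongest case is that the effect may be small. At 5–10% removal and gaps up to 0.5 SD, type I error is only 5.2–5.9%, and power falls no further than 78.1%. An acceptance–outcome correlation of 0.3 implies a gap of 0.58 SD (10% removed) or 0.52 SD (20% removed). A 1 SD gap needs a correlation of about 0.51 to 0.57. That stands: the 1 SD column is an upper scenario. It does not conflict with the adjustment figures, because the share of the shift remaining does not depend on that correlation.

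High removal may also be unlikely. Preexisting physical or cognitive limitations that would hinder app use are excluded in both arms, the platform has been trialled in these patients, and nurses give instruction. This bears on the 5–20% assumption, but unwillingness to use the technology is a separate trigger that arises later.

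The removal sentence sits in a risk statement and does not say that collected data are discarded or that the chart audit stops. This is fair, but removal from the study is the wording, and nothing elsewhere keeps these patients in the analysis.

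Outcomes are not equally exposed. Opioid totals come from the chart audit and could be kept if authorization still covers it. Baseline knowledge scores exist and could be used for adjustment. Neither replaces discharge surveys that were never collected.

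Finally, the study is quasi-experimental with one unit per arm and lists its endpoints as not applicable. Unit differences will remain whatever is done here, so the error rates above isolate this one mechanism. That does not justify adding an avoidable bias.

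**Conclusion.** The concern holds. Followed as written, the plan makes a one-sided selection after assignment and has no analysis that undoes it. Its size cannot be read from the documents. Under the assumed ranges the shift is 0 to 0.20 SD and type I error runs from 5.0% to about 18–19%, or 20.2% if removals are replaced. Mid-range values (0.5 SD gap, 10–20% removed) give 5.9–8.3%. The loss of power is secondary. Adjustment for technology comfort can reduce the shift, but it is conditional in the plan and does not restore the removed patients.

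This should be settled before enrolment. Under Data Collection Procedure, "At the time of discharge the patient will complete the Revised American Pain Society Patient Outcomes Questionnaire", before leaving the unit. If removed patients are not surveyed then, no later analysis can recover their responses.

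**What to change.** Leave the move to standard education as it is. Change what it means for the data:

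- State that stopping the iPad is not removal from the study. Patients who still consent complete the discharge APS-POQ-R and PPQ and have the chart audit.
- Make the main analysis the comparison by assigned unit, including those who stopped the iPad.
- For patients who withdraw consent, collect nothing further and count them by arm.
- Report how many stopped the iPad, the reasons and how many withdrew consent. Where consent allows, compare baseline technology comfort and PPQ scores between stoppers and continuers.
- Label any accepters-only analysis as secondary.

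The cost is a few sentences. The surveys and chart audit are already planned for every participant, and keeping all assigned patients leaves 64 per arm and 80.1% power at d = 0.50. Some who stop the iPad may decline further data collection, so some data will still be missing. The estimated effect may be diluted by non-users; it then describes assignment to the iPad unit rather than use of the iPad.

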
Study Design and Methods

Methods: *Describe, in detail, the research activities that will be conducted under this protocol:*

Variables

The independent variable is the type of patient education deliverable given to the two study arms, group A (experimental group, real-time, interactive, mobile education system) and group B (control group, standard of care). The dependent variables are 1) patient knowledge, 2) patient perceived participation in pain management, 3) high and low pain scores, and 4) total opioid consumption. A simple table of the independent, dependent, and additional variables are presented in Appendix B. A detailed accounting of all data points including variable type, theoretical definitions, and operational definitions can be found in the detailed code book.

Method

Design

This prospective study has been designed as quasi-experimental study. This study design was selected for several reasons. This study seeks to explore both a treatment and control group in efforts to compare outcomes which are dependent on the type of intervention. To control for fidelity of the intervention and avoid cross over, behavior changes from nurses providing the intervention, the intervention the patient receives will be determined by the location they are bedded in hospital. Orthopedic TJA patients are assigned at random and based on bed availability to one of two patient care units. One of the two patient care units will offer standard education the other unit will offer the mobile, iPad based education. The patient care unit to offer the mobile, iPad based education will be selected at random. This study design will help minimize will reduce the risk of selection bias, increase fidelity of the intervention, and increases the probability that the differences demonstrated between the study groups will be attributed to the actual intervention under study.

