Study participants will be assigned into one of two study arms, intervention or control, based on random assignment to the two designated units. At the time of consent, patients will be informed that there are two study arms and that some subjects will receive enhanced pain management education; however, subjects will not explicitly be informed if they are in the intervention or control arm of the study. Participants who have verbally consented will receive a HIPAA authorization form accompanied by a letter reminding them of the study and their consent to participate at the time of the preoperative visit. This typically occurs one to two days before surgery. Participants will be asked to sign the HIPAA authorization form and return the clinical staff. Participants will be provided an extra copy for their records. No Patient data will be collected prior to this. Once HIPAA has been signed participants will complete the intake survey provided with the packet of information.

Researchers are blinded to the study arm the participant was enrolled in until after consent has been obtained, the patient is enrolled in the study, and has been admitted to the hospital and assigned a bed. Once enrolled and consented, bed control will be notified to assign the patient(s) to one of the two designated patient care units with no specific direction offered on which unit the patient(s) should be assigned to. The only direction provided will be to split the patients evenly between the two units. Only ten study arm participants may be enrolled and active at one time. This is limited based on the number of available iPad devices for the purposes of this study.

Study Population

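### Blinding the researcher does not prevent trait-related assignment, because bed control chooses the unit with only an even-split instruction and no random sequence or concealment is described

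*Combined protocol and SAP*

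**What the plan says.** All of this is in the combined protocol and SAP.

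- **Who is blinded** (Recruitment and Consent): "The researcher will remain blinded to the type of education delivery that the patient will receive until after enrolment and bed assignment". The next sentence draws the conclusion: "This will prevent potential bias with inadvertently assigning patients to groups based on characteristics, like age".
- **Who assigns** (Design): "Once enrolled and consented, bed control will be notified to assign the patient(s) to one of the two designated patient care units". On how to choose, the plan adds: "The only direction provided will be to split the patients evenly between the two units".
- **What the unit means** (Design): "the intervention the patient receives will be determined by the location they are bedded in hospital".
- **How placement is described** (Design): "Orthopedic TJA patients are assigned at random and based on bed availability to one of two patient care units". One further random step is named: "The patient care unit to offer the mobile, iPad based education will be selected at random".
- **Device limit** (Design, Setting): at most ten participants can be active in the iPad arm at a time.
- **Analysis** (Data Analysis Plan): the groups are to be examined for baseline differences that may need control. The only between-group method named is an independent t-test, or a nonparametric analysis if normality fails.

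**The concern.** The party that is blinded is not the party that allocates. Blinding the researcher cannot affect how bed control chooses between two units.

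Bed control does not need to know which unit has the iPads, or to favour either arm, for bias to arise. Ordinary bed management is enough. If one unit tends to receive older patients, revisions or longer expected stays, the arms differ on those traits because unit and arm are the same thing. The even-split instruction equalises numbers, not characteristics, so a perfectly even count is compatible with unlike groups.

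At stake is whether a difference in pain, knowledge, participation or opioid use can be credited to the education. The sentence in Recruitment and Consent tells readers that this threat has been dealt with, and the Limitations section does not mention it.

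**Working it through.** **1. The passages side by side**

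| Question | Plan's answer | Section |
|---|---|---|
| Who is blinded? | The researcher, until after enrolment and bed assignment | Design; Recruitment and Consent |
| Who picks the unit? | Bed control, after consent and enrolment | Design |
| By what rule? | Even split only | Design |
| What does the unit decide? | The arm | Design |
| What is drawn at random as a separate step? | Which of the two units gets the iPads | Design |
| Is there a patient-level sequence or concealment? | None described | – |
| Is bed control masked? | Not stated | – |

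The claim would follow only if the researcher chose the unit, or if bed control followed a concealed sequence. The plan describes neither. Drawing the iPad unit at random is one draw between two units; it does not make the patients on those units alike.

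**2. The plan's own figure**

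Inputs (Sample Size): d = 0.50, power 0.80, alpha 0.05. The exact two-sided t-test needs 63.77 per arm, rounded up to 64, with power 0.801 at 64. The stated 64 reproduces and is not in dispute. It is used below.

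**3. Illustration of size**

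The steering fractions and correlations are assumptions; the documents give no figures for either. Let a standard normal risk score describe each patient. A fraction p at highest risk all go to one unit, and the rest fill in to equal numbers. That unit then holds a fraction 2p of high-risk patients and the other holds none.

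Difference in mean risk = 2p × m(top) + (1 − 2p) × m(rest) − m(rest) = 2p × [m(top) − m(rest)]

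- p = 10%: m(top) = 1.755, m(rest) = −0.195. Difference = 0.2 × 1.950 = 0.39 SD.
- p = 5%: m(top) = 2.063, m(rest) = −0.109. Difference = 0.1 × 2.171 = 0.217 SD.

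Bias in the outcome = correlation × difference. The noncentrality of the t-test is bias / √(2/64), with 126 degrees of freedom. With no true effect, the two-sided rejection rates are:

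| Steered | Correlation | Bias (SD) | False-positive rate |
|---|---|---|---|
| none | any | 0 | 5% |
| 5% | 0.3 | 0.065 | about 6.5% |
| 5% | 0.5 | 0.109 | 9.4% |
| 10% | 0.3 | 0.117 | 10.1% |
| 10% | 0.4 | 0.156 | 14.1% |
| 10% | 0.5 | 0.195 | 19.5% |

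**4. How often availability may decide**

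Setting gives 50 beds and more than 9,000 orthopedic admissions a year. At full occupancy that allows at most 50 × 365 / 9,000 = 2.03 bed-days per admission. Setting also foresees patients relocated because of high census. Length of stay is not given. If it is near two days, there may often be a bed on only one unit.

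**The case against.** The strongest defence has four parts.

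- **Researcher blinding has real value.** Consent is taken about two weeks before surgery, and the researcher learns the arm only after bed assignment. That limits selective enrolment and steering by the researcher, and the sentence can be read as meaning only this. This stands. A reader might infer that the plan gives no protection at all, and the documents do not support that.
- **The documents do not say that bed control knows the arms.** The staff training described under Management of interventions does not mention bed control. This also stands. The supportable statement is that no masking is described, not that bed control is unmasked. The concern survives because placement by trait biases the comparison even if bed control is unaware of the arms.
- **Predictability is not established.** A reader might infer that an even split makes each placement foretell the next. The plan does not say how strictly the split is kept. If one guesses the unit with fewer patients so far, the guess is right 75% of the time under balance within pairs, 71% within fours, 62% within groups of 20, and 55% if balance holds only over all 128. Strict alternation would also leave little room for the free steering assumed above. The weakness is discretion, not predictability.
- **The study is labelled quasi-experimental and plans a baseline check.** Age, comfort with technology, anxiety, chronic pain, preoperative opioid use and mental health conditions are collected. This is genuine mitigation, but partial. No adjustment model or covariate set is named, and unlisted traits such as frailty cannot be checked or controlled.

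**Conclusion.** The concern holds in a limited form. The plan credits researcher blinding with preventing trait-related assignment, but bed control makes the assignment, with an even-split instruction and no described sequence or concealment. Blinding covers enrolment and the researcher's own conduct. It does not cover the choice of unit.

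The size in this trial is unknown. The range of about 6.5% to 20% false positives assumes that every patient in the top 5% to 10% of risk goes to one unit, a correlation of 0.3 to 0.5 with the outcome, and no adjustment. With no steering the rate is 5%. These figures show what modest steering could do; they are not evidence that steering will occur. The mismatch between the claim and the mechanism rests on the text alone and needs no assumption. It should be corrected.

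**What to change.** 1. **Narrow the claim.** In Recruitment and Consent, limit the sentence to selective enrolment and steering by the researcher. In Design, do not describe unit placement as random unless a sequence is used.
2. **Use a concealed list where a choice exists.** When both units have a bed and an iPad is free, bed control follows a pre-generated, concealed 1:1 list in permuted blocks of varying size, prepared outside bed control.
3. **Handle the other cases openly.** When only one unit has a bed or all ten iPads are in use, place by availability. Record the placement and its reason as not randomised, report how many there are, and add a sensitivity analysis without them.
4. **Adjust.** In the Data Analysis Plan, adjust the group comparison for pre-specified baseline variables already collected, for example age, comfort with technology, preoperative opioid use and procedure.

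**Cost.** One list, one field recording the reason for placement, an adjusted model and a few changed sentences; no extra patients. Someone must hold the list, and staff time under Resources is limited. Bed control must follow the list when both units are open, and it still reports whether they are, so some discretion remains. If availability often decides placement, the sensitivity set may be small; the reported count will show this.
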